**Aim 2: Compare patient weight loss and diabetes-related outcomes among those who receive obesity screening and counseling to those who do not, following implementation of preventive service coverage.** We will examine post-policy impact of obesity screening and counseling in a cohort of patients with diabetes and at high risk for diabetes. Specific outcomes to be examined include weight loss, diabetes incidence, and diabetes outcomes (including hemoglobin A1c, controlled blood pressure, use of a statin medication). Further, we will determine patient characteristics, including demographics (age, race/ethnicity, rurality), and practice characteristics, including provider type, and their impact on receiving/providing obesity screening and counseling. Understanding patient and practice characteristics most likely to engage in obesity counseling can identify best practices and inform how to increase engagement by both patients and providers.

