## 2.0 Background

### 2.1 Scientific Background and Gaps

Overweight and obesity are America's number one health concern. The prevalence of obesity in the US is greater than 36%, which is far above the Healthy People 2020 objective of less than 30.5%. Perhaps most concerning is the rate that obesity has increased, having doubled since 1970. As the second most preventable cause of death, obesity is a risk factor for diabetes, cardiovascular disease, stroke, and cancer, all major causes of death in the US. Addressing obesity through lifestyle interventions decreases the risk of developing type 2 diabetes, a disease which affects over 29 million people (9.3% of the US population). Diabetes is associated with serious complications, including cardiovascular disease, blindness, renal failure and lower extremity amputation. Although complications are preventable with proper medical and lifestyle management, including weight loss, nearly half of patients with diabetes do not have adequate glycemic control.

Primary care clinics may be an ideal setting for weight control interventions. Greater than 80% of Americans see a PCP regularly and access to primary care is expected to increase with health care reform. Further, as PCPs identify and treat the multitude of conditions affected by being overweight, including diabetes, they are ideally positioned to best engage their patients in weight management. The Centers for Medicare and Medicaid Services (CMS) implemented a healthcare procedure coding system code for intensive behavioral therapy (IBT) for obesity within primary care settings in 2012 to facilitate payment for addressing obesity, which was followed by universal coverage by insurers for IBT for adults of all ages in 2013. However, the impact of this coverage on patient-centered outcomes is largely unknown.

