***Diabetes Cohort Definition.*** During year 1 of the proposed project, the investigative team, in collaboration with the PaTH Network, will identify a valid cohort of patients with type 2 diabetes. The cohort of patients under study will be defined as all patients age 18 and older with an indication of type 2 diabetes during the proposed study time frame. Patients will be classified as having diabetes using a clinically validated algorithm: type 2 diabetes mellitus on the problem list, diabetes-specific medications, hemoglobin A1c (HbA1c) results > 7.0%, or one inpatient diagnosis code or two outpatient diagnosis codes for type 2 diabetes (ICD-9 codes 250.xx). The diabetes cohort will be further limited to patients who will likely be captured in the PaTH EHR records or claims data so that outcome assessments can occur. Thus, we will further limit the diabetes cohort to patients who have either: (1) had at least 2 outpatient primary care visits in one of the PaTH health systems in the past 3 years (since January 1, 2012), or (2) for whom claims data are available. The cohort will be dynamic, with new patients added into the cohort after 2015 as they meet the diabetes cohort definition prospectively. The observational period for the outcome variables will be for the 10-year period from 2009-2019, thus including 3 years of data prior to the first policy change (CMS instituting coverage for intensive behavioral therapy for obesity) and 3 years after the last policy change (Pennsylvania Medicaid expansion) under study.

Following the definition of the diabetes cohort and key diabetes outcomes and covariates as described above, an initial extraction of variables will be conducted in Year 2 of the proposed project for years 2009-2015. This early data extraction from the PaTH Network will allow for cohort validation and data cleaning and editing, as well as required programming and determination of the analysis models. We will utilize this initial data extraction in Years 2 and 3 to analyze the impact of early health policy changes, as well as to prepare a manuscript of both the protocol and early findings of policy impact. The final data extraction will occur during the final quarter of Year 4 of the proposed project, allowing for completion of a ten-year time period (2019).

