Furthermore, we will use the similar models as described above to evaluate post-policy impact of obesity screening and counseling (number of visits) on the outcomes such as weight loss, diabetes incidence, and diabetes outcomes (including hemoglobin A1c, controlled blood pressure, use of a statin medication). The outcome data collected after the universal coverage change (i.e.,  $t = 0, 1, \dots, 6$ ) will be used to estimate the trend of change. The number of screening and counseling will be used as a predictor in the mixed effects models. The effects of patient and practice characteristics will also be examined in the models. Statistical software SAS 9.4 and R environment will be used to implement the proposed analyses.

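### The Aim 2 counseling models use only 2013-2019 outcomes and name no prior outcome as a covariate, so a pre-existing trend difference can be read as a counseling effect

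*Combined protocol and SAP*

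**What the plan says.** Aim 2 (Section 1.0) is to "Compare patient weight loss and diabetes-related outcomes among those who receive obesity screening and counseling to those who do not". The paragraph of Section 8.0 that serves it says that models similar to the policy models will be used. "The outcome data collected after the universal coverage change", given as t = 0 to 6, "will be used to estimate the trend of change". It adds: "The number of screening and counseling will be used as a predictor in the mixed effects models". It does not say whether visits act on the level, the slope or both, or whether the count varies over time. Patient and practice characteristics are also to be examined.

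Section 7.2 sets a longer data period for both cohorts: "The observational period for the outcome variables will be for the 10-year period from 2009-2019". Section 2.1 dates the two coverage steps: a CMS code for "intensive behavioral therapy (IBT) for obesity within primary care settings in 2012", then "universal coverage by insurers for IBT for adults of all ages in 2013".

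**The concern.** The policy model in Section 8.0 is justified by its control for where patients started and how they were already changing. The counseling models lose that control, because a window starting at t = 0 has no pre-period from which to estimate an earlier slope. They are also the models that need it most, since patients and providers decide who is counseled. A patient already gaining weight, or already losing it, may be more likely to be counseled, and the later difference in slope would then be credited to counseling.

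The sample size gives no protection. The Statistical Power paragraph says that very small effects will be detectable and relies on clinical judgment of significant results. That judgment can tell a small effect from a large one, but not a confounded effect from a real one.

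**Working it through.** **1. The window.** The documents state no sample-size calculation, alpha or target effect, so the only plan figure to reproduce is t = 0 to 6. Set against data "for the 10-year period from 2009-2019":

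| Year of t = 0 | Window | Earlier years held |
|---|---|---|
| 2012 | 2012-2018 | 3 |
| 2013 | 2013-2019 | 4 |
| 2014 | 2014-2020 | 5 |

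Only 2013 ends with the data, and it is the year of universal coverage in Section 2.1. The outcomes for 2009-2012 are therefore held but not used.

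**2. Does another part of the plan fill the gap?**
- The individual-level exposure variables in Table 1 are sociodemographics and co-morbidities. No prior outcome is named.
- The propensity score list in Section 8.0 names no prior outcome. That analysis is secondary and targets the policy effect, not counseling received.
- The random effects have mean zero for all patients, so a slope that differs systematically by counseling status goes into the counseling term.

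**3. Trend.** Let d be the prior difference in slope (counseled minus uncounseled), p the fraction of it that persists after 2013, and e the true effect. The post-only counseling-by-time term estimates p × d + e. Simulation inputs, all assumed: 25% counseled, random-intercept SD 15 kg, slope SD 0.8 kg/yr, residual SD 2.5 kg, p = 1, and 100 runs of 5,000 patients.

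| d (kg/yr) | e (kg/yr) | p × d + e | Post-only estimate | All-years segmented estimate |
|---|---|---|---|---|
| 0 | 0 | 0 | 0.003 | -0.003 |
| -0.2 | 0 | -0.2 | -0.197 | -0.003 |
| +0.2 | 0 | +0.2 | +0.203 | -0.003 |
| -0.2 | -0.3 | -0.5 | -0.497 | -0.303 |
| +0.2 | -0.3 | -0.1 | -0.097 | -0.303 |

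The Monte Carlo standard error is 0.003. The last two rows also carry a 5 kg level difference. With visits as a cumulative count and no true effect, the coefficient was -0.076 or +0.079 kg per visit for d = -0.2 or +0.2.

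**4. Level.** A 5 kg prior difference with no trend difference gave 5.09 kg when counseling was a plain main effect. The counseling-by-time slope was 0.003 with or without it, and the cumulative-visit coefficient was 0.004 against 0.001.

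**5. Persistence.** Subtracting a patient's own earlier slope estimates p × d + e - d, which is e - (1 - p) × d. That is unbiased only if p = 1. A second set of assumptions was used here: 400,000 patients, 4-5% counseled, no true effect, slope SD 0.3-0.5 kg/yr, residual SD 2 kg, and log-odds of counseling rising 0.25-0.5 per SD of prior weight and of true prior slope.

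| p | Post-only (kg/yr) | Own prior slope subtracted (kg/yr) |
|---|---|---|
| 1 | +0.07 to +0.24 | about 0 |
| 0.5 | +0.03 to +0.12 | -0.05 to -0.11 |
| 0 | about 0 | -0.08 to -0.24 |

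If selection acts on the observed, noisy prior slope, subtraction gives roughly -0.2 to -0.5 kg/yr through regression to the mean.

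**6. Precision of subtraction, under the inputs of step 5.** The slope noise variance is 2²/28 over seven post years, and 2²/5, 2²/2 or 2²/0.5 over four, three or two earlier years. The ratio of standard errors, subtracted to post-only, is √[(4/28 + 4/S) / (SD² + 4/28)] with S = 5, 2 or 0.5. It is 1.5-2.0 with four years, 2.3-3.0 with three and 4.6-5.9 with two.

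**7. Detectability, under the inputs of step 3.** The SD of a seven-year slope is √(0.8² + 2.5²/28) = 0.929. At N = 320,000 and two-sided alpha 0.05 (assumed), the difference with 90% power is (1.960 + 1.282) × 0.929 × √(1/n1 + 1/n0). That is 0.054 kg/yr if 1% are counseled and 0.018 if 10% are.

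**8. Prior mean and slope as covariates.** Under the inputs of step 5 this never increased the bias. It removed most of it when selection was on observed history, but only about 5-18% when selection was on the true underlying slope. The reason is noise: the reliability of a four-year slope is 0.09/(0.09 + 0.8) = 0.10 to 0.25/(0.25 + 0.8) = 0.24.

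**The case against.** The best defense is that the paragraph restricts outcome data and does not forbid a prior outcome as a covariate. Patient characteristics and co-morbidities are adjusted for, subject-level random effects carry over, and the propensity list is open-ended. This stands in part: the listed covariates may remove some of the bias. But no prior outcome is named anywhere, and the propensity analysis has a different target.

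Four stronger readings are tempting, and the documents do not support them.
- A reader might infer that prior level differences are always read as counseling effect. The paragraph speaks of a trend of change, and weight loss in Table 1 is already a change from the first counseling visit. Level leaks only under a plain main effect, which is permitted but not stated.
- A reader might infer that 2009-2012 holds the only information separating history from effect. A patient first counseled in 2016 has 2013-2015 outcomes before counseling inside the window, and Section 8.0 allows time-dependent covariates. The plan specifies no use of those years, however.
- A reader might take the simulated kilograms as the bias in this study. They follow from assumed inputs and shrink to about zero if slopes do not persist.
- A reader might conclude that the 2009-2019 segmented contrast should be the main analysis. It assumes full persistence. When that fails and counseled patients had been gaining faster, it produces a spurious benefit, in the direction the study hypothesizes. It also breaks at 2013 rather than at first counseling, and it cannot serve diabetes incidence.

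The earlier records are also not complete. Eligibility requires primary care visits only since January 2012, or claims data, and later entrants to the dynamic cohorts may have no earlier years. For Medicare patients, 125,412/328,455 = 38% of the diabetes table in Section 7.2, coverage began in 2012, which leaves at most three clean years.

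**Conclusion.** The point holds in a limited form. The Aim 2 counseling models use 2013-2019 outcomes only and name no adjustment for a patient's earlier outcome, so a prior difference in trend can pass into the counseling estimate. A prior difference in level can do so only if visits enter as a plain main effect.

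The size cannot be stated, because the documents give no counseled share, slope SD, slope persistence or selection strength. Under full persistence the whole prior trend difference passes through; under none, about nothing does. A spurious 0.2 kg/yr, if present, would almost certainly be statistically significant at the planned sample size. This should be corrected before the counseling models are fitted. It does not by itself show that the results would be wrong.

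**What to change.** Amend the counseling paragraph of Section 8.0 as follows.
- For continuous and yearly binary outcomes, add as covariates each patient's mean and slope of that outcome before first counseling, or before a matched index date for uncounseled patients, using records from 2009 onward.
- Enter visits as a time-varying count, and say whether the count acts on level, slope or both.
- For diabetes incidence, use prior weight or BMI and its trend, because patients free of diabetes have no earlier event.
- Plot pre-counseling trends by later counseling status.
- Keep patients without earlier records in the main model, with a missing-history indicator or imputation, and repeat the analysis in those with records.
- Use a 2009-2019 segmented model with a counseling-by-change-in-slope term only as a sensitivity analysis. State its persistence assumption, and treat 2012 as post-coverage for Medicare patients.

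The data are already to be extracted, so the cost is modest extra analysis and some loss of precision. Earlier records will be incomplete for some patients. Confounding will remain, because short, noisy slopes adjust only partly, and the report should say so.

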## 1.0 Objectives

The overarching goal of this proposal is to understand the comparative effectiveness of obesity counseling as covered by Centers for Medicare and Medicaid Services (CMS) in improving weight loss for adults either with or at high risk of type 2 diabetes. CMS and most insurers now include obesity screening and counseling benefits, with no cost sharing to patients. Since overweight patients are at highest risk for diabetes, improved weight management services could prevent diabetes and its negative health outcomes. Beneficiaries with obesity are eligible for up to 20 face-to-face visits for weight counseling in the primary care setting. We propose comparing weight and diabetes outcomes in three states using electronic health record (HER) and claims data before and after this policy was implemented. The PaTH network brings together six academic health systems – the University of Pittsburgh/University of Pittsburgh Medical Center, Penn State College of Medicine/Hershey Medical Center, Temple University School of Medicine/Temple Health, and the Johns Hopkins University/Johns Hopkins Health System/Johns Hopkins Health Care, Geisinger Health Systems, and The University of Utah – to function as an integrated research network and learning health system, providing an infrastructure for observational studies, such as the one proposed here, that require populations beyond a single health system to answer important patient-centered health services questions ([www.pathnetwork.org](http://www.pathnetwork.org)). Using the PaTH Clinical Data Research Network (CDRN) infrastructure, we propose the following specific aims:

**Aim 1: Evaluate the impact of universal preventive service coverage for obesity screening and counseling on weight loss, diabetes incidence, and diabetes outcomes, in patients with diabetes or at high risk for diabetes (defined by body mass index (BMI)  $\geq 25$ ).** We will determine how the annual probability of receiving obesity and/or nutritional counseling (as defined by Current Procedural Terminology (CPT) code) changed pre- and post-policy across all insurers in a cohort of patients with diabetes and at high risk for diabetes. We hypothesize that individual patients are more likely to receive counseling following coverage implementation. Further, we hypothesize that patients who receive a greater number of face-to-face visits will have greater weight loss compared to those who receive fewer visits.

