**Table 1. Proposed Outcomes for the Pre-diabetes and Diabetes Cohorts**

Outcomes	Definition	Notes
Pre-diabetes cohort		
Weight loss during counseling	Weight lost from first IBT visit to final IBT visit	Available at all PaTH sites
Weight loss maintenance	% of weight lost during program and maintained over remaining time period, reported by year	Available at all PaTH sites
Diabetes incidence	% of patients who develop diabetes per year following weight counseling	Available at all PaTH sites
Patient-reported outcomes	-SF-12 -PHQ-2, PHQ-8, PHQ-9 -Physical function -sleep -fruit and vegetable consumption -social support -physical activity -PROMIS (PROMIS 29, physical function, depression) -healthy lifestyles -patient reported medication reconciliation	Available at some sites – Formal inventory of PROs will be collected at each institution at the beginning of the project, to be included as secondary outcomes
Diabetes cohort		
Weight loss during counseling	Weight lost from first IBT visit to final IBT visit	Available at all PaTH sites
Weight loss maintenance	% of weight lost during program and maintained over remaining time period, reported by year	Available at all PaTH sites
Patient reported outcomes	-SF-12 -PHQ-2, PHQ-8, PHQ-9 -Physical function -sleep -fruit and vegetable consumption -social support -physical activity -PROMIS (PROMIS 29, physical function, depression) -healthy lifestyles -patient reported medication reconciliation	Available at some sites – Formal inventory of PROs will be collected at each institution at the beginning of the project, to be included as secondary outcomes
Uncontrolled diabetes	Average A1c > 9 or no A1c	Available at all PaTH sites
Controlled blood pressure	SBP < 140, DBP < 90, averaged across values over year	Available at all PaTH sites
On a statin medication	Evidence of a statin medication on current EHR medication list	Available at all PaTH sites
Receiving annual eye exam	Documentation of eye exam once in past year	Available at all PaTH sites
Receiving annual urinary microalbumin test	Documentation of lab testing for urinary microalbumin at least once in past year	Available at all PaTH sites
Lower extremity amputations	Documentation of procedure for lower extremity amputation or billing code through health plans in past year	Available at all PaTH sites

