where  $\mathbf{x}_{mijk}$  is the vector of regressors for the fixed effects,  $\boldsymbol{\beta}_m$  is the corresponding vector of fixed-effects parameter coefficients,  $\mathbf{z}_{ij}$  is a vector of cluster-level regressors for the random effects for the  $j^{\text{th}}$  cluster of the  $i^{\text{th}}$  state,  $\boldsymbol{\gamma}_{1ij}$  is the cluster-level random-effect coefficients and is common to all  $m$ , and  $\boldsymbol{\gamma}_{2mijk}$  is the subject-level random-effect coefficients associated with the parameter  $\beta_m$  for the  $k^{\text{th}}$  subject within the  $j^{\text{th}}$  cluster. The random effects are assumed to follow a multivariate normal distribution with mean zero. Because the vector  $\mathbf{x}_{mijk}$  may include subject-level, cluster-level and state-level exposure variables, the fixed effects parameter vectors  $\boldsymbol{\beta}_1$  and  $\boldsymbol{\beta}_2$  represent the effects of different exposure variables on the annual changes in the pre- and post-periods. Thus, we may perform statistical tests to examine whether there are differences in trends between the pre- and post-periods overall and for each state, and whether the patterns of changes differ between the states.

Similarly for a count outcome  $Y_{ijkt}$  (e.g., number of clinical visits), we define the expected value  $\mu_{ijkt} = E(Y_{ijkt})$  and apply a Poisson regression model based on the natural log link function. The log expected number of clinical visits,  $\log(\mu_{ijkt})$ , can be modeled with the aforementioned segmented mixed-effects model. The use of an offset term in the models yields the estimates of the rate of clinical visits rather than the mean number of visits. The fixed-effect parameters,  $\beta_1$  and  $\beta_2$ , represent the effects of exposure variables on the annual changes in log of incidence rates for the pre- and post-periods, respectively. For a continuous outcome  $Y_{ijkt}$ , we will model the mean,  $\mu_{ijkt} = E(Y_{ijkt})$ , with the mixed-effects model and the parameters  $\beta_1$  and  $\beta_2$  indicate the effects of exposure variables on the annual changes in the outcomes for the pre- and post-periods, respectively. All final statistical models will be assessed with respect to the goodness-of-fit and the appropriateness of model assumptions. Statistical software SAS 9.4 and R environment will be used to implement the proposed analyses.

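### The counseling analysis names only a visit count as exposure, so Aim 2's any-versus-none contrast has no term of its own and, if uncounseled patients are included, a per-visit effect can appear without any dose effect

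*Combined protocol and SAP*

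**What the plan says.** Section 1.0 sets two different questions. Aim 1 hypothesizes that "patients who receive a greater number of face-to-face visits will have greater weight loss compared to those who receive fewer visits". Aim 2 compares outcomes "among those who receive obesity screening and counseling to those who do not, following implementation of preventive service coverage". The benefit makes patients "eligible for up to 20 face-to-face visits for weight counseling in the primary care setting", so the count can run from 0 to 20.

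Section 8.0 uses one analysis to "evaluate post-policy impact of obesity screening and counseling (number of visits) on the outcomes such as weight loss, diabetes incidence, and diabetes outcomes". Its exposure is given in one sentence: "The number of screening and counseling will be used as a predictor in the mixed effects models". The section does not say whether the count is linear, categorized or smoothed, or whether patients with no visits are in the model. The only pointer to form is the general model, where a covariate vector "is the vector of regressors for the fixed effects".

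Nothing else in Section 8.0 supplies an any-versus-none exposure. Receipt of counseling is listed there as a binary variable, but as an outcome. The propensity-score analysis is directed at the overall policy effect.

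Table 1 defines weight loss during counseling as "Weight lost from first IBT visit to final IBT visit" and counts incident diabetes per year after weight counseling.

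**The concern.** More versus fewer visits and any versus none are different estimands, and a single count coefficient cannot deliver both. If zero-visit patients are in the model, as Aim 2 requires, the coefficient blends the gap between zero and any visits with the gradient among those who had visits. If they are left out, Aim 2 has no analysis.

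Counseling is not randomized, so receivers and non-receivers may differ for reasons unrelated to the visits. Section 8.0 expects enough power to detect very small effects in more than 320,000 and 2,000,000 patients. At that size even a modest constant difference could produce a significant per-visit coefficient and be taken as a dose response. The planned review of clinical significance judges how large an effect is, not whether it reflects dose.

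**Working it through.** **No figure to reproduce.** The plan gives no alpha, effect size, SD, counseling uptake or visit distribution. Only the cohort totals in Section 7.2 can be checked: the site counts sum to 328,455 and 2,062,499, as printed.

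**Slope when the truth is a pure step.** Suppose receivers differ from non-receivers by a step d, and extra visits do nothing. Let u be uptake, and m and v the mean and variance of visits among receivers. The least-squares slope on the count is

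slope = d·u·m·(1−u) / [u(v+m²) − u²m²] = (d/m) × w, where w = (1−u)m² / [(1−u)m² + v].

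Here w is the weight that the zero-versus-any contrast carries in the slope. All inputs below are assumptions, with d = 1 kg. Slopes are absolute values; the direction is weight loss.

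| u | m | v | w | slope, kg per visit |
|---|---|---|---|---|
| 0.05 | 3 | 9 | 8.55/17.55 = 0.49 | 0.1425/0.8775 = 0.162 |
| 0.01 | 2 | 3 | 3.96/6.96 = 0.57 | 0.0198/0.0696 = 0.284 |
| 0.10 | 4 | 16 | 14.4/30.4 = 0.47 | 0.36/3.04 = 0.118 |
| 0.10 | 2 | 16 | 3.6/19.6 = 0.18 | 0.18/1.96 = 0.092 |

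Over u = 0.01-0.10, m = 2-4 and v = 3-16 the slope runs from 0.09 to 0.28 kg per visit. The true dose effect is zero throughout. The slope scales with d, so it is 9% to 28% of whatever step is assumed.

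**Would it be significant?** Further assumptions: N = 320,000, SD 8 kg, visits between 1 and 20, d = 1 kg. With uptake of 1-20%:

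- mean 2.0 visits: slope 0.31-0.33 kg per visit
- mean 3.9 visits: slope 0.14-0.15
- mean 10.5 visits: slope about 0.07

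The z values range from 5.4 to 24. In simulation (100 runs per scenario, uptake 1% and 5%) the count-only slope was significant at the two-sided 5% level in every run. The same fit understates the any-versus-none effect: at the mean visit count it predicts 0.54-0.77 kg instead of 1.0.

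**Separating the two contrasts.** In the same simulations, the count slope estimated alongside an any-visit indicator averaged −0.004 to 0.006 kg per visit. It was significant in 1-8% of runs, in line with 5% given 100 runs.

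**Trend model.** A small random-slope run (4,000 patients, 20% uptake, mean 3.9 visits) gave receivers an extra annual change of −0.5 kg and no dose effect. The count-by-time coefficient was −0.066 alone, close to the expected 0.136 × 0.5 = 0.068 in size, and −0.002 once the indicator was added. The variance components were not recovered well, so its standard errors are not relied on.

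**Which outcomes.** Never-counseled patients have no first or final IBT visit and no start point for incidence after counseling. For those two Table 1 outcomes they cannot enter the model. A1c, blood pressure and statin use exist for everyone, as would a yearly weight.

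**The case against.** A reader might infer that the plan commits to a linear term and will report a counseled-versus-uncounseled gap as a dose response. The documents do not say so. Form and zero-handling are unstated, linearity is only the default reading of a numeric regressor, and Section 8.0 promises a check of fit and assumptions that could expose a step. That check is generic, however, and would not supply the missing Aim 2 contrast.

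A reader might also infer that Aim 1's weight-loss hypothesis would be declared supported without a test. Under Table 1 that does not follow: uncounseled patients have no weight-loss value, so the count slope would already compare more with fewer visits among receivers. The problem for that outcome is the opposite one, that Aim 2 has nothing to compare.

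Nor does the slope come mostly from the zero-versus-any gap. In the first three scenarios above that gap carries 47-57% of the weight, and in the fourth only 18%.

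Finally, the arithmetic is cross-sectional least squares, whereas the plan models level and annual change. If the count enters both equations, a constant level difference loads on the intercept and does not distort the trend. This stands as a limit: to distort the trend coefficient, the groups must differ in annual change. The mixing then occurs within whichever equation holds the difference.

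**Conclusion.** The point holds in conditional form. Section 8.0 specifies one exposure for two questions and leaves its form and the handling of zero-visit patients open. On neither reading can one count coefficient serve both aims.

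For A1c, blood pressure, statin use, or weight measured yearly in everyone, a receiver/non-receiver difference in level or annual change can appear as a per-visit effect with no dose effect behind it. For a 1 kg step this is roughly 0.1 to 0.3 kg per visit at 1-10% uptake and a mean of 2-4 visits. The size rests entirely on assumed inputs and a least-squares approximation; on the logit scale the proportions are only approximate. The direction does not depend on the inputs. For weight loss and incidence as defined in Table 1, Aim 2's contrast is not estimable.

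**What to change.** **Aim 2.** Fit a model with an any-versus-none counseling indicator and no count. Alternatively, use a two-term model with indicator coefficient b and coefficient c for visits beyond the first, and report the receiver average b + c(m−1), where m is the mean number of visits among receivers. The indicator in the two-term model must not be reported alone as the Aim 2 effect: it estimates exactly one visit versus none. Define weight change and incidence so that they also apply to uncounseled patients, for example yearly EHR weight from a common index date.

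**Aim 1.** Test visit count, in categories or as a spline, among counseled patients only or as a term next to the any-visit indicator. Base the dose conclusion on that term alone. State how zero-visit patients are handled in each model.

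**Cost.** This needs some extra analysis work and an outcome definition for the uncounseled. The dose estimate draws its precision from counseled patients only: with N = 320,000, SD 8 kg, 1% uptake and visit variance 2, its standard error is 8/√(320,000 × 0.01 × 2) = 0.10 kg per visit. The change separates the two contrasts; it does not remove selection from either.
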